Another complementary approach that has been used successfully to build PCP knowledge and skills and enhance provider communication is group PCP-specialist clinical tele-videoconferencing (CTV) sessions. These sessions provide participating PCPs with serial patient-based advanced education by exposing them, over time, to a depth and breadth of cases and issues within a defined clinical area. Prior to each session, PCPs submit data on patients about whom the PCPs are seeking diagnostic and/or therapeutic management advice from a multidisciplinary specialist team. The team reviews the submitted information prior to the session. During the scheduled session, a specialist team at a "hub" facility and PCPs at multiple "spoke" locations see and hear each other (via CTV) and engage in a real-time discussion about the management of the submitted patient cases. The specialist team, in addition to giving recommendations, discusses the evidence and/or rationale behind the recommendations, thereby increasing the session's educational value. The PCP who submitted the consult, as well as other PCPs participating in the session, interact with the specialist team, asking clarifying questions. The specialist team also provides a brief didactic relevant to the cases discussed. Such sessions have been shown, in one setting and condition, to improve PCP capacity to manage complex patients and positively affect patient care outcomes. Specifically, University of New Mexico implemented such a program for management of patients with hepatitis C, and, in a controlled trial, showed that PCPs who engaged in group CTV sessions with hepatologists improved patient access and achieved clinical outcomes comparable to those of the hepatologists. 38,39

We hypothesize that *DWHP Support* will improve the quality and efficiency of WH care in CBOCs.

Our specific aims are:

Aim #1: To evaluate the effect of *DWHP Support* on WH care quality and efficiency, using a stepped wedge design;

Aim #2: To explore the impact of *DWHP Support* in changing DWHP behavior and self-rated WH knowledge, skills, and self-efficacy;

Aim #3: To assess attitudes about *DWHP Support* and its use, specialist time for its implementation, and other features that could influence *DWHP Support's* effectiveness, sustainability and spread;

Aim #4: To develop tools to measure quality of WH care in VA.

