% of episodes of care with fully proficient care quality and efficiency Control Intervention (effect size)		25 episodes per DWHPper study arm* ICC=0.03 ICC=0.05		50 episodes per DWHPper study arm* ICC=0.03 ICC=0.05	
80%	90% (medium)	14	18	10	14
67%	83% (medium)	8	10	6	8
67%	77% (small)	22	28	16	22
50%	63% (very small)	16	20	12	16

^{*}study arm refers to intervention versus control, and includes all data collection

Aim #2:

We hypothesize that *DWHP Support* will increase DWHPs' practice expertise, and thereby modify their practice behavior, resulting in improved quality and efficiency (the focus of Aim 1). To test this hypothesis, we will collect process outcomes for the components of the intervention and their effects on patient care with a SCAN/e-consult referring provider survey (here after referred to as e-consult survey).

Provider Behavior: e-consult referring DWHP brief surveys: We will obtain the names of participating providers who initiate gynecology e-consults by obtaining from CDW, through VINCI, a list of all participating site gynecology e-consults. After each e-consult has been completed, we will email a request for the providers who initiated the consult to complete a brief survey about the encounter, including if and how it impacted their management plan. More specifically, we will ask: to what extent the consult altered the diagnostic, patient counseling, and/or treatment plans for this patient; the provider's confidence in their ability to implement the recommended diagnostic, patient counseling and/or treatment plans; how much, if at all, the provider learned something from the consult; and how, if at all, the consult affected the provider's plans to refer the patient for an in-person consultation. For the referring provider surveys, we will use the question about effect on the provider's plans to refer the patient to separately estimate number of avoidable consults averted by the availability of e-consults. An open-ended question, asking for additional comments, will also be included. The e-consult referring provider survey will be administered online (using Inquisite software) and responses will be confidential.

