Self-rated WH knowledge, skills, and self-efficacy: DWHP self-assessment tool: Prior to the start of *DWHP Support, or early in its implementation,* and again after at least 12 months of use by study providers, we will administer a self-assessment tool to all DWHPs to assess their self-rated WH knowledge, skills, and self-efficacy in delivery of WH care. The self-efficacy assessment is modeled after the WVHSHG mini-residency self-evaluation tool, which examined 15 clinical content areas using a 5-point Likert scale. The 12-month self-efficacy assessment will be expanded to add items for clinical content areas covered during the SCAN sessions. We will also assess perceived change in self-efficacy in WH delivery, and perceptions about influences on this change. We will generate summary descriptive statistics for each of the data fields assessed.

Aim #3: To assess attitudes about DWHP Support and its use, specialist time for its implementation, and other features that could influence DWHP Support's effectiveness, sustainability and spread.

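### Aim 2 concerns change in DWHPs' self-ratings at two waves, but the plan gives only descriptive summaries, with no linked before/after estimate and no measure of uncertainty

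*Combined protocol and SAP*

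**What the plan says.** The combined protocol and SAP describes Aim 2 in three places.

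- **Research Aims** words it as exploring the impact of DWHP Support "in changing DWHP behavior and self-rated WH knowledge, skills, and self-efficacy". Table 1 repeats the idea of change and schedules the self-assessment at baseline and during implementation.
- **Aim #2** gives a directional hypothesis, that DWHP Support "will increase DWHPs' practice expertise, and thereby modify their practice behavior". It continues: "To test this hypothesis, we will collect process outcomes for the components of the intervention and their effects on patient care". The instrument named at the end of that sentence is the e-consult referring provider survey.
- **Self-rated WH knowledge, skills, and self-efficacy** describes the self-assessment tool. The first wave comes before the start of DWHP Support "or early in its implementation"; the second is described as "and again after at least 12 months of use by study providers, we will administer a self-assessment tool to all DWHPs". The self-efficacy part is modelled on a tool covering 15 content areas on a 5-point Likert scale. The 12-month form "will be expanded to add items for clinical content areas covered during the SCAN sessions". Perceived change in self-efficacy is also asked about. The analysis is one sentence: "We will generate summary descriptive statistics for each of the data fields assessed".

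**The concern.** Giving the same instrument to the same providers twice is useful mainly for measuring change. Followed to the letter, the analysis sentence yields a set of summaries for each field at each wave. It does not say that a DWHP's two responses will be linked, that a difference will be calculated, how precise that difference would be, or what happens to a DWHP who answers only once.

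Two things are at stake. First, any difference between two separate summaries mixes real change with a change in who answered. Second, with few DWHPs, ignoring the pairing discards precision. Linkage also has to be arranged when the data are collected. If the responses cannot be matched, the within-DWHP change cannot be recovered later.

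**Working it through.** **No figure to reproduce.** Aim 2 states no sample size, SD, effect size or precision, so the first check is of the text.

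**Does another section supply the missing estimate?**

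- Aim #1 Statistical Analysis: the stepped-wedge model is for episodes of care nested within DWHPs, not for self-ratings.
- Aim #3, Qualitative Data Analysis: the comparison across DWHPs and over time is of interviews, not of scores.
- Aim #2, e-consult survey: it asks how much the provider learned and how plans changed, but reaches only providers who initiated an e-consult.
- Aim #2, self-assessment: perceived change is collected, as a retrospective self-report.

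None of these is a before/after contrast of the self-assessment scores across DWHPs.

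**What pairing is worth.** The inputs are assumptions:

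- n = 20 DWHPs answering both waves. The documents give about 20 DWHPs per study arm, but only for Aim 1, so 15 and 40 are shown as well.
- Item SD = 0.8 at each wave on the 5-point scale. The documents give no SD. Every result below scales in proportion to it.
- Within-person correlation r = 0.3, 0.5 or 0.7. The documents give none.

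Formulas for the standard error (SE) of the mean change:

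- pairing ignored: √(2 × SD² / n)
- paired: √(2 × SD² × (1 − r) / n)

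For n = 20:

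- ignored: √(2 × 0.64 / 20) = √0.064 = 0.253
- r = 0.3: √(0.064 × 0.7) = 0.212
- r = 0.5: √(0.064 × 0.5) = 0.179
- r = 0.7: √(0.064 × 0.3) = 0.139

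| n | Pairing ignored | r = 0.3 | r = 0.5 | r = 0.7 |
|---|---|---|---|---|
| 15 | 0.29 | 0.24 | 0.21 | 0.16 |
| 20 | 0.25 | 0.21 | 0.18 | 0.14 |
| 40 | 0.18 | 0.15 | 0.13 | 0.10 |

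The variance falls by the fraction r, that is by 30%, 50% or 70%. At n = 20 the approximate 95% CI half-width is 1.96 × 0.253 = 0.50 points if pairing is ignored and 1.96 × 0.179 = 0.35 points when paired with r = 0.5.

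**What a change in responders can do.** Again by assumption, let 20 DWHPs answer wave one, let nobody's score change, and let 5 lower-scoring DWHPs not answer wave two. If those 5 scored d points below the other 15, the wave-two mean exceeds the wave-one mean by (5/20) × d:

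- d = 0.4: 0.25 × 0.4 = 0.10 points
- d = 0.8: 0.25 × 0.8 = 0.20 points

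The paired change among the 15 who answered twice is zero in both cases. At d = 0.8 the spurious gain is about the size of the standard errors above. The documents give no non-response figure for this tool, so this shows a mechanism and does not forecast its size.

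**The case against.** The strongest defence is that the formal aim is to *explore*, and descriptive statistics suit an exploratory secondary aim. That stands against any demand for a hypothesis test or p-value. It does not remove the need for an estimate: exploring an impact on changing scores still calls for the size of the change and how uncertain it is.

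Three stronger readings are tempting, and the documents do not support them.

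- *A reader might infer that the plan promises a test of the self-assessment scores and then omits it.* The sentence about testing names the e-consult survey, not this tool. What remains is that Research Aims says *explore* while Aim #2 says *test*.
- *A reader might infer that change is never measured.* Perceived change is collected and falls under the descriptive summaries, and the e-consult survey asks about learning. These are weaker than a before/after contrast, but they do bear on change.
- *A reader might infer that the second form makes the waves incomparable.* Items are added and no removal is stated, so a common set appears to remain. No overall average is planned either, and reporting by field keeps new items apart. The risk arises only if someone later averages across all items.

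It is also fair to say that the plan does not rule out linkage, and that n, SD and correlation in the illustration are assumed. Both points stand. They limit what can be said about size, not the fact that no linked estimate is specified.

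Finally, a paired interval would sit on an uncontrolled before/after contrast whose first wave may fall after implementation began. That is correct. Such responses could already include some effect, most likely pulling the estimated change toward zero, so the fix has to deal with them.

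**Conclusion.** The point holds in a limited form. The self-assessment is collected twice from all DWHPs to serve an aim about change, yet the plan specifies no within-DWHP before/after estimate, no measure of uncertainty and no handling of one-wave responders. The perceived-change questions and the e-consult survey only partly fill that gap.

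On the illustrative assumptions (20 DWHPs at both waves, item SD 0.8, r from 0.3 to 0.7), using the pairing takes the standard error from 0.25 to between 0.21 and 0.14. That the stated analysis gives no linked contrast rests on the text alone; the size of the gain rests on the assumptions.

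This should be changed because it is cheap and linkage cannot be added afterwards. It is not critical: the aim is secondary and exploratory, and the Aim 1 result does not depend on it.

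**What to change.** Add a short analysis paragraph under the self-assessment heading of Aim #2:

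1. Link each DWHP's two responses by study code.
2. On the items common to both waves, report mean within-DWHP change with a 95% CI, or fit a mixed model with a DWHP random effect so that one-wave responders contribute. Define the set as the common items rather than as 15 items, because the plan says only that the tool is modelled on one with 15 content areas. Report how many DWHPs answered each wave and both.
3. Report follow-up-only items and perceived change separately and descriptively, and keep them out of any change score.
4. Flag first-wave responses collected after implementation began, and repeat the estimate without them.
5. Keep the planned descriptive tables.
6. Reconcile *explore* in Research Aims with *test* in Aim #2.

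The cost is slightly more analysis and the need for linkable responses. No extra data collection is required.

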Aim #4: To develop tools to measure quality of WH care in VA.

To complete the work in Aim 1, we will need to develop tools to measure the quality of WH care in VA. VA monitors two gender-specific quality indicators as part of its annual External Peer Review Program performance monitoring – timely receipt of breast and cervical cancer screening. Though relatively easy to measure, there is little variation in these quality indicators across VA sites. ⁷⁶ Therefore, we have selected alternate gynecology tracer conditions for our quality assessment. Explicit evidence-based quality guidelines exist for each of the selected tracer conditions (abnormal uterine bleeding; ⁵⁵⁻⁵⁸ counseling in patients prescribed teratogenic medications, contraception counseling and management; ^{60,61} preconception counseling; ⁶⁶⁻⁶⁸ menopause management, and urinary incontinence. ⁶⁹). The goal of Aim 4 is to operationalize these guidelines into quality measurement tools. The process for achieving this aim consists of four steps – translating guidelines, defining CPRS data sources and elements, developing EMR abstraction forms, and creating computer programs based on specifications. ⁷⁷ Serial testing and revising will be done within each step.

Translating Guidelines: We will first construct, modify, or augment the algorithm for each guideline. Next, we will translate each guideline into a series of binary "if/then" statements. The will also define terms as needed for clarifying these if/then statements. Two investigators will independently draft these "if/then" statements for each guideline and then reconcile their statements, discussing differences, to form for each guideline one draft series of if/then statements. To validate these if/then statements, these drafts and the guidelines and algorithms associated with them will then be given to members of our quality measurement tool validation, who will comment on our interpretation of the guidelines (to create the algorithm and specify terms) and our if/then statements, and then back-translate them to reconstruct quality guidelines. There are discrepancies between the versions reconstructed by our panel members, and the actual guidelines, we will investigate the source of these discrepancies and modify/clarify our if/then statements as needed. We will do this serially until we have a final set of validated if/then statements and associated definitions.

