clarity. After we make this initial revision, we will ask the nurse abstractor to use the form to abstract data from the EMRs of 10-20 patients (identified via the same process as the initial 10-20 patients, using ICD9 and CPT codes while working on the VINCI server platform), asking questions when needed and noting difficulties. We will revise the form based on this feedback and then re-test serially until all problems are resolved. We will also develop training materials for our nurse abstractors.

Creating computer programs to operationalize specifications: Finally, we will create a program, using STATA 11, to operationalize the specifications and algorithms. As needed by our if/then statements, this will include variable construction, such as converting linear variables (e.g. age) to bivariates/categorical (e.g., >30 years of age or ≤30). Then we will develop programs to operationalize the algorithms formed with the if/then statements to make a final determination of whether or not the care was guideline adherent (as a yes/no determination). For each episode of care, all relevant if/then statements must reflect the guideline-adherent action in order for that episode of care to be classified as guideline-adherent. For cases in which the program determines the care to not be adherent, the program will also specify where in the algorithm the care failed to be guideline adherent. We will test and validate this program for a sample of 25 cases in each condition, by having an investigator who is blinded to the computer determination, review the information entered into the abstraction form and determine if the care was adherent, and if not, identify where it was non-adherent. We will compare these manual determinations to those of the computer, correcting any errors in the programming that may be revealed by the discordances. The investigator will also have both the EMR chart extract and the completed chart abstraction form, to determine if all of the pertinent information is in the form to allow him/her to make an accurate decision.

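### The back-translation check on the if/then statements is not independent of the source: panel members receive the guidelines and comment on them before they reconstruct them, so agreement is weak evidence that the statements are faithful.

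*Combined protocol and SAP*

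**What the plan says.** The procedure is in the combined protocol and SAP, Aim #4, under Translating Guidelines. Two investigators each draft a series of if/then statements "for each guideline and then reconcile their statements, discussing differences". To validate the result, "these drafts and the guidelines and algorithms associated with them will then be given to members of our quality measurement tool validation". The panel members are those "who will comment on our interpretation of the guidelines" "and our if/then statements, and then back-translate them to reconstruct quality guidelines". The signal for revision named after that step is a mismatch: where there are "discrepancies between the versions reconstructed by our panel members, and the actual guidelines, we will investigate the source of these discrepancies", and the statements are changed as needed. The loop then repeats: "We will do this serially until we have a final set of validated if/then statements and associated definitions".

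The paragraph on creating computer programs, later in Aim #4, sets the scoring rule. For an episode of care to count as adherent, "all relevant if/then statements must reflect the guideline-adherent action". The same paragraph describes a check on 25 cases per condition, in which an investigator blinded to the program's result makes a manual determination that is compared with it.

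**The concern.** Back-translation is informative because the person reconstructing the original works only from the translation. If the translation has lost an exception or moved a threshold, the loss appears in the reconstruction. A member who has just studied and commented on the source can supply the missing piece without noticing. The reconstruction then matches the guideline although the statement does not.

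The likely error runs one way. The plan ties revision to discrepancies, so anything that suppresses them favours calling the set validated too early.

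The statements matter because they feed the Aim 1 main outcome, quality of care defined as guideline adherence, and scoring is all-or-none. One misstated statement can change the class of a whole episode, in either direction: a wrongly strict statement fails adherent care, and an omitted condition can pass non-adherent care. Building sound measurement tools is also the stated purpose of Aim #4 itself.

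**Working it through.** The plan gives no panel size, agreement threshold or detection rate for this step, so there is no stated figure to reproduce. The check is a reading of the order of steps.

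1. **What members hold when they start.** Drafts, guidelines and algorithms arrive together (Translating Guidelines). Nothing says that the guidelines are withheld, or withdrawn before the reconstruction.

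2. **Who does which task.** One sentence gives both tasks to the same people in sequence: comment, "and then back-translate them to reconstruct quality guidelines". No separate group of back-translators is described.

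3. **What the comparison can show.** Let *d* be the chance that a misstatement would show as a discrepancy if members worked from the statements alone. Let *f* be the share of those discrepancies that disappear because members fill the gap from the source. By definition, the sensitivity of the step as written is

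   sensitivity = *d* × (1 − *f*).

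   If *f* = 0, exposure to the source costs nothing. If *f* = 1, the step detects nothing. The documents fix neither *d* nor *f*. The order of tasks allows *f* above 0, and reversing the order largely removes that route.

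4. **Whether another step fills the gap.**
   - *Independent double drafting* guards against one drafter's slip. A misreading that both investigators share survives reconciliation.
   - *The comment task* is a direct comparison of statement with guideline and can reveal a misstatement. It is an open read-through, whereas back-translation was added as a further test.
   - *Defining CPRS data sources and elements* and *Developing chart abstraction forms* test data sources, forms and rules, not fidelity to the guideline.
   - *The 25-case check* is blinded to the program's result, not to the guideline, and its stated remedy is to correct programming errors. The plan does not say whether the investigator judges adherence against the guideline or against the if/then statements. If the former, a misstatement could surface as a discordance. If the latter, both determinations would carry the same misstatement.

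5. **How far a surviving error could reach.** Only a subset of the statements is carried forward to abstraction. The Aim 1 section on guideline-adherent care names three tracer conditions, while Aim #4 lists six. A misstatement in a statement that is not used cannot affect Aim 1. One in a statement that is used acts through the all-or-none rule.

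**The case against.** The strongest reply is that back-translation is the third layer of checking and that the other two are substantial. Two investigators draft independently. Panel members then compare the statements with the guideline directly, which is arguably the best way to spot a wrong threshold and cannot be done without the source. Members are also asked to back-translate the statements, and someone who does that faithfully will still produce a discrepancy when a condition is missing. All of this stands.

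It defeats a stronger reading that a reader might infer: that the check cannot expose a misstated statement, or passes whether or not the statements are right. The documents support only reduced sensitivity by an unknown amount, not zero sensitivity. Nor do they support saying that the 25-case check has no bearing, since its benchmark is not stated.

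Two further cautions also stand. Whether the same members serve in later rounds is not stated. The text around this step is visibly broken, so wording may have been lost; no criticism is made of that.

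The objection does not answer the narrower point. The plan added back-translation as a separate test, and as ordered that test is not separate from the source it is meant to recover.

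**Conclusion.** The point holds in a limited form. As written, the back-translation is not independent of the guidelines. Its sensitivity to omitted or misstated conditions is reduced by an amount that the documents do not allow anyone to estimate, and agreement should not be reported as independent validation. The comment step and the double drafting give partial protection; the 25-case check is not a clear backstop.

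A reader might try to turn this into lost power for Aim 1 by assuming that some share of episodes is misclassified and reworking Table 2. The documents do not support that step. Such a figure would price the existence of a bad statement, not the added chance that one survives because of the task order. The share and direction of misclassification would also be pure assumption. No effect on the Aim 1 estimate is claimed here.

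The conclusion assumes that the order of tasks in the text is the order used. If the panel in fact reconstructed without the source, one clarifying sentence settles the matter. This is a cheap improvement, not a fault that undermines the outcome.

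**What to change.** Reverse the order of the panel's tasks in Translating Guidelines:

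1. Give members only the if/then statements and the term definitions, and have them back-translate.
2. Collect and lock the reconstructions.
3. Compare them with the actual guidelines and record the discrepancies.
4. Only then release the guidelines and algorithms, and ask for comments on interpretation and on the statements.

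For later rounds of a guideline, use members who have not yet been given its source where the panel is large enough. The documents do not give the panel size, so this part is conditional; where it is not possible, report those rounds as unblinded.

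The main change is a small edit to the protocol, with the same panel and the same tasks. Each round may take slightly longer. The blind will be imperfect because members may know the guidelines from practice, but they would no longer be handed the source before reconstructing it.
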